- End of Study (EoS): 1) After all the subjects complete their study conclusion contact, occurring within 30 days of the projected study conclusion date of the last enrolled subject, that is, 14 months (approximately 430 days) from the enrolment date of the last subject; In case criteria for VE analyses are not met during this period, the follow-up will be extended and 2) the release of all polymerase chain reaction (PCR) test results for the HZ rash lesion samples.

Refer to **glossary of terms** for the definition of EoS.

- Study groups:

Table 8 Study groups, treatment and epochs foreseen in the study

Study groups	Targeted number of eligible subjects	Age (years)	Epochs	
			Epoch 001	Epoch-002
RZV group	3069	≥50 years	•	•
Placebo group	3069	≥50 years	•	•

Table 9 Study groups and treatment foreseen in the study

Treatment name	Vaccine/Product name	Study Groups	
		RZV	Placebo
RZV	VZV gE	•	
	AS01B	•	
Placebo	Lyophilized sucrose		•
	Saline (NaCl) solution for reconstitution		•

- **Control:** Placebo-controlled
- **Vaccination schedule:** 0 and 2 months

- **Treatment allocation:** Eligible subjects will be randomized (1:1) to RZV group or Placebo group. The randomization algorithm will use a stratification procedure accounting for age (50-69 YOA and \geq 70 YOA).
- Blinding:

Table 10 Blinding of study epochs

Study Epochs	Blinding
Epoch 001	observer-blind
Epoch-002	observer-blind

- Sampling schedule:

- CCI
[REDACTED]
[REDACTED]
[REDACTED]

- Clinical specimens of HZ lesions will be collected from all subjects who are clinically diagnosed with a suspected case of HZ (Section 8.3.2).
- A urine specimen will be collected from all female subjects of child-bearing potential (see [glossary of terms](#) for definition of woman of child bearing potential) at Visit 1 (Day 1) and Visit 2 (Month 2).

Note: The result of the pregnancy test must be obtained before any study vaccination and must be negative.

- **Data collection:** standardized Electronic Case Report Form (eCRF). Solicited and unsolicited AEs will be collected using a subject Diary (paper Diary [pDiary]). In the event of suspected HZ, the HZ clinical course will be collected using a HZ-specific diary card.

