8.3.3. Follow up of suspected HZ cases (Amended, 23 November 2020)

Data will be collected on all suspected HZ cases that occur from Visit 1 (Day 1) until the study conclusion. For each suspected case of HZ that the investigator concludes is clinically consistent with HZ, data will be collected weekly until Day HZ-29 and weekly from Day HZ-30 until the HZ rash resolves. If the rash hasn't resolved the subject will be seen weekly until the rash resolves. The end date of the pain associated with this HZ episode should be recorded. At the time of LSLV, if a subject has an ongoing HZ case, he/she will be followed up till Day HZ-29.

The investigator will note in the subject's eCRF the end date of HZ rash and if any HZ-associated symptoms are still ongoing. Complications of the HZ episode (for example, PHN, disseminated HZ, ophthalmic disease) should be recorded as AE/SAE, as appropriate. *(Amended, 23 November 2020)*

If pain reappears in the same area after a 4-week pain-free period and is not accompanied by a new HZ rash, it will be assigned to the previous HZ-episode.

The presence of a new rash will be considered a new episode. Visits/contacts will start from Day HZ-1 defined as the first visit following appearance of the new rash.

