10. STATISTICAL CONSIDERATIONS

10.1. Sample size determination

This study is planned to enroll approximately 6138 subjects equally randomized (approximately 3069 subjects) to the RZV and Placebo groups.

The sample size of the study has been determined to have at least 90% power for the confirmatory VE primary objective of $\geq 25\%$ (LL of the 2-sided 95% CI of VE).

Based on the assumption of a true conservative VE of 85% (reference ZOSTER-006 study) for prevention of confirmed HZ cases during the 12 months of follow-up post second dose, a total number of 27 cases of HZ will be needed to demonstrate with at least 90% power that the lower limit (LL) of the 2-sided 95% confidence interval (CI) for the VE is above 25% (By Pass 2012, One Proportion Power Analysis, one-sided test, one-sided alpha=2.5%). In case the number of confirmed HZ cases required for VE evaluation are not met, the follow-up duration will be extended.

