10.1.2. Sample size calculation

Table 22 shows the power achieved with the target sample size (2762 evaluable subjects per group) with a randomization ratio of 1:1 to demonstrate the primary objective of VE under the alternative hypothesis that with true VE at 85%, lower limit of 2-sided 95% CI of VE observed will be $\geq 25\%$ (Pass 2012, One Proportion Power Analysis, one-sided test, one-sided alpha=2.5%).

An attack rate of HZ of 0.85% per year in the Placebo group, a drop-out rate of 5% and an incidence of 5% for non-compliance to vaccine schedule were assumed for sample size calculations.

Table 22 Sample size and expected number of cases in ZOSTER-076

Endpoints	Vaccine efficacy		Expected Number of HZ confirmed cases		Attack rate in control	Sample Size		Power
	VE - assumed	VE - LL of 95% CI	Placebo	All		Evaluable	Enrolled*	
HZ confirmed	85%	25%	23	27	0.85%	5524	6138	At least 90%

*By PASS 12, One Proportion Power Analysis, one-sided test, one-sided alpha=2.5%. *Assuming 10% drop out or non-evaluable subjects

The following conditions are planned prior to the final HZ VE analyses of the study. The number of HZ cases mentioned refers to the cases in the primary cohort for efficacy (i.e. the mES).

1. At least 27 confirmed HZ cases for the overall HZ VE analysis.
2. All subjects will be followed up till the last enrolled subject completes 12 months follow-up post last vaccination. In case the 27 cases needed for VE analysis are not accrued during this period, the follow-up will be extended.

CCI

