7. INTERIM ANALYSES

7.1. Sequence of analyses

The analysis of all primary and secondary endpoints will be performed when all data up to study conclusion are available. A clinical study report (CSR) will be written at this stage and individual listings will be included.

One final analysis is planned and will be triggered when the following will take place:

- When at least 27 confirmed cases of HZ have accrued in the primary cohort for efficacy (cut-off date for primary efficacy analysis); AND
- When all subjects have completed at least 12 months safety follow-up post last vaccination.

Data contributing to the analysis of the primary efficacy objective (confirmed HZ cases) will be collected until the cut-off date. After the cut-off date, case confirmation of any new suspected HZ will not be performed. Once the study reaches the cut-off date, the conclusion contact for a subject will be planned based on the status of the safety follow-up:

- **Cut-off date reached before the completion of safety follow-up** – Continue the monthly safety follow-up after the cut-off date until all subjects have completed 12 months of follow-up post last dose.
- **Cut-off date reached after the completion of safety follow-up** – Continue the monthly contacts after the completion of the 12 months safety follow-up period until at least 27 confirmed HZ cases have accrued (cut-off date).

When the trigger for primary efficacy analysis is reached, subjects with an ongoing HZ episode will be followed until Day HZ-29.

The conclusion contact of the last subject will be the study end.

If the data for exploratory endpoints become available at a later stage, (an) additional analysis/ analyses will be performed. These analyses will be documented in the annex study report.

Description	Disclosure Purpose (CTRS=public posting, SR=Study report, internal)
Final	Public disclosure, Study report

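### SAP 7.1 ends confirmation of herpes zoster (HZ) cases at an at-least-27-case cut-off, although the protocol and SAP 5.5.1.1 count cases to study end; the change is not declared and may cost events

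*SAP*

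**What the plan says.** **SAP 7.1 (Sequence of analyses).** The single final analysis is triggered when two things have happened: at least 27 confirmed cases in the primary efficacy cohort, and at least 12 months of safety follow-up after the last dose for every subject. The first is labelled the cut-off date for efficacy, and primary-endpoint data are collected only until then. The section continues: "After the cut-off date, case confirmation of any new suspected HZ will not be performed". It plans for the cut-off falling before safety follow-up is complete; monthly contacts then continue for safety. Study end remains the last subject's conclusion contact.

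**SAP 5.5.1.1 and protocol 10.3.3.1.** Both define the primary endpoint window as running from 30 days after dose 2 to study end.

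**Protocol 10.1.2.** Two conditions precede the final VE analysis. One is at least 27 confirmed mES cases. The other reads: "All subjects will be followed up till the last enrolled subject completes 12 months follow-up post last vaccination". Follow-up is extended if 27 has not been reached; nothing shortens case counting if it has.

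**Protocol 8.3.3 and 5.2.** "Data will be collected on all suspected HZ cases that occur from Visit 1 (Day 1) until the study conclusion". End of Study requires "the release of all polymerase chain reaction (PCR) test results for the HZ rash lesion samples".

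**SAP section 8**, which lists changes to the protocol-defined analysis, is silent on the cut-off. **SAP 9.2.1** ends time at risk for event-free subjects at their last visit or contact, with no censoring at the cut-off.

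**The concern.** The protocol uses 27 as the minimum information needed before analysis. SAP 7.1 also uses it as the point at which endpoint ascertainment may end. The two uses give the same analysis only if the 27th case comes after the last subject's 12 months. If it comes earlier, subjects stay under blinded follow-up with monthly contacts, but a new suspected episode is not taken through PCR or the HZ Ascertainment Committee (HZAC) and cannot become a primary event.

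The same confirmed cases feed the primary VE, the VE at 50-69 and at 70 years and over, and the complementary analysis on the exposed set, so all of these lose events. The final analysis has to wait for 12-month safety in any case, so ending confirmation early does not bring it forward.

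The SAP also conflicts with itself. Section 5.5.1.1 counts to study end, section 7.1 stops at the cut-off, and section 9.2.1 lets person-time run to last contact. Applied literally, the numerator stops at the cut-off and the denominator does not.

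**Working it through.** **1. Reproduce the plan's own figure.** Protocol 10.1 states that "a total number of 27 cases of HZ will be needed to demonstrate with at least 90% power", for true VE 85%, a lower limit (LL) above 25% and one-sided alpha 2.5%; 10.1.2 adds a placebo rate of 0.85% per year and 2762 evaluable subjects per group.

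- Expected cases in one year: 2762 × 0.0085 = 23.5 placebo, plus 23.5 × 0.15 = 3.5 vaccine, total 27.0.
- Share of cases in the vaccine group: 0.75/1.75 = 0.4286 at VE 25%; 0.15/1.15 = 0.1304 at VE 85%.
- Exact binomial test with 27 cases: success if at most 6 are in the vaccine group. Exact alpha is 0.0216 and power 0.9465 (94.7%).

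The stated figure holds, so stopping at 27 keeps the stated power.

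**2. Cases expected by the planned end.** The average rate over both groups is 0.0085 × 1.15/2 = 0.0048875 per person-year, so 27 cases need 27/0.0048875 = 5524 person-years. mES time at risk starts 30 days after dose 2, so the last enrolled subject contributes about 11 months by the planned end. With uniform enrolment over R months (assumption) and no further loss, the mean is 11 + R/2 months:

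cases = 5524 × (11 + R/2)/12 × 0.0048875

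| R (months) | Expected cases | Beyond 27 | Share of total | 27th case before planned end |
|---|---|---|---|---|
| 0 | 24.7 | none | – | not reached |
| 4 | 29.2 | 2.2 | 8% | about 1 month |
| 6 | 31.5 | 4.5 | 14% | about 2 months |
| 12 | 38.2 | 11.2 | 29% | about 5 months |

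**3. Which R the documents support.** The centre table in SAP 9.2.3 gives first-subject dates from 14 May 2021 to 15 September 2021. Enrolment therefore spanned at least about 4 months. No passage gives its full length, so 6 and 12 months are assumptions.

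**4. Sensitivity to incidence.** Protocol 3.2 gives a range of 3.2 to 8.6 per 1000 person-years. At 3.2 the expected total is 11.0 (R = 4) to 14.4 (R = 12). Then 27 is not reached in the planned period and nothing is lost.

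**5. Effect on precision.** Exact conditional 95% limits for VE, equal time at risk in both groups:

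- 4 of 27 cases in the vaccine group: VE 82.6%, LL 49.1%.
- 5 of 38 cases in the vaccine group: VE 84.8%, LL 60.9%.

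This pair shows the 12-month case, the upper end of the table.

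**6. Numerator and denominator.** If cases stop at the 27th while person-time runs to last contact (SAP 9.2.1 as written), incidence in both groups is understated by about 8% (R = 4) to 29% (R = 12). The rate ratio, and so VE, is roughly unaffected.

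**The case against.** The strongest reply is that this is an ordinary event-driven cut-off. It is absent from the SAP's list of Amendment 1 changes, so it appears to date from the February 2021 version, before the first listed subject visit. The protocol's person-year definition in 10.3.3.1 mentions a cut-off date for the analysis. Protocol 10.1.2 can be read as a trigger and not as a counting window. SAP 7.1 says at least 27, so it does not strictly cap the count. Suspected episodes after the cut-off would still be listed.

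Much of this is fair. An event-driven cut-off is a legitimate design and nothing suggests it was chosen on results. But the protocol never defines its cut-off date as the 27th case, and the endpoint window in both documents still runs to study end. If the cut-off may fall after the 27th case, the SAP does not say when, and confirmation still ends whenever it is declared. A listing of suspected episodes does not supply confirmed events.

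A reader might also infer more than the documents support:

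- *That required cases will be discarded.* The loss arises only if 27 cases come before the last subject's 12 months, and those cases are left unconfirmed, not deleted.
- *That power suffers.* It does not at the planning assumption. At VE 75%, which is not a protocol assumption, power is 71% at 27 cases, 64% at 29 and 78% at 38. The pattern reflects the discreteness of the exact test, so a 27-versus-38 contrast is not a fair measure of harm.
- *That the conclusion at 70 years and over is endangered.* That analysis is descriptive, with no lower-limit criterion. With few cases the limit is unstable: 1 versus 5 gives LL -79%, 1 versus 6 gives -37%, 1 versus 8 gives +7%.
- *That VE would no longer cover 12 months.* The 27 cases correspond to 5524 person-years in 5524 evaluable subjects, an average of one year. Late enrollees have less, but unequal follow-up is part of the design.

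**Conclusion.** The contradiction stands. SAP 7.1 cannot be followed together with SAP 5.5.1.1 and protocol 10.3.3.1 if 27 cases accrue early, and section 8 does not declare the departure from the protocol.

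The size is conditional. At the design rate, with the roughly 4 months of enrolment that the documents support as a minimum, about 2 of 29 cases would go unconfirmed, in about the last month. The figure of about 11 of 38 needs 12 months of enrolment, which is an assumption. At the low end of the protocol's incidence range the loss is nil. All of these figures assume uniform enrolment, VE 85% and no further loss to follow-up.

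What is lost is precision and completeness in the primary, age-specific and exposed-set estimates. The primary test keeps its stated power. This should be corrected, but it does not undermine the primary conclusion.

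**What to change.** In SAP 7.1:

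1. Delete the sentence that ends case confirmation.
2. Define the efficacy cut-off as the later of the 27th confirmed mES case and completion of the 12-month follow-up.
3. Confirm by PCR or HZAC, and count, every suspected case up to that date.

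In SAP 9.2.1, end time at risk at the same date, and use it for the primary, age-stratum and exposed-set VE.

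The cost is SAP wording, plus PCR and HZAC review of a few more episodes that the protocol already requires to be sampled and referred. There may be a short wait for the last results before database lock; the documents do not show that lock would be unaffected.

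If the sponsor prefers the early cut-off, the alternative is to list it in SAP section 8, bring the endpoint window in SAP 5.5.1.1 into line, state exactly when the cut-off falls, and censor time at risk at it in 9.2.1. That removes the contradiction but gives up the later events.

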7.2. Statistical considerations for interim analyses

No interim analysis will be performed.

8. CHANGES TO THE PROTOCOL DEFINED STATISTICAL ANALYSIS

Following is the change from protocol defined statistical analysis:-

- Fatal SAEs will not be tabulated using the date of death within the same time periods.
- **CC1**
- *Grade 3 for redness/swelling will be defined as redness/swelling with diameter ≥ 100 mm in Chinese scale*
- *Preferred Terms to identify Grade 4 for swelling and redness have been added*
- *The analysis on at least 1 local AE (solicited and unsolicited; solicited only) with at least 1 general AE (solicited and unsolicited; solicited only) and with any AE (solicited and unsolicited; solicited only) during the solicited follow-up period with causal relationship with vaccine and AE rated as at least grade 3 according to GSK and Chinese scale will not be performed.*

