	
Serious Adverse Events (SAEs) (Amended, 23 November 2020)
 
 – Occurrence and relationship to vaccination of SAEs from Day 1 up to 30 days post last vaccination. – Occurrence and relationship to vaccination of SAEs from Day 1 up to 12 months post last vaccination. – Occurrence of SAEs related to study vaccine, from Day 1 up to end of study. – Occurrence of SAEs related to study participation or to GlaxoSmithKline concomitant medication/vaccine during the entire study period. – Occurrence and relationship to vaccination of fatal SAEs from Day 1 up to 30 days post last vaccination. – Occurrence and relationship to vaccination of fatal SAEs from Day 1 up to 12 months post last vaccination. – Occurrence of related-fatal SAEs from Day 1 up to end of study. 
pIMDs (Amended, 23 November 2020)
 
 – Occurrence and relationship to vaccination of pIMDs from Day 1 up to 30 days post last vaccination. – Occurrence and relationship to vaccination of pIMDs from Day 1 up to 12 months post last vaccination. – Occurrence of related serious pIMDs after 12 months post last vaccination up to study end.

Exploratory

CCI

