	
The percentage of subjects with at least 1 report of unsolicited AE (including cellulitis) classified by MedDRA and reported within 30 days (Days 1-30) post-vaccination period will be tabulated with exact 95% CI. The same tabulation will be performed for grade 3 unsolicited AEs, for unsolicited AEs with a relationship to vaccination, grade 3 unsolicited AEs with a relationship to vaccination.
 
Number and percentage of any, grade 3, related, grade 3 related and medically-attended adverse events reported within 30 days (Days 1-30) post-vaccination period according to MedDRA primary preferred terms.
 
Number and percentage of SAEs from first vaccination up to 12 months post last vaccination will be presented with 95% CI. The same tabulation will also be done for the interval starting from first vaccination up to 30 days post last vaccination.
 
Number and percentage of SAEs causally related to vaccination for the interval starting from first vaccination up to 30 days post last vaccination and from first vaccination up to 12 months post last vaccination and from study start up to study end will be presented with 95% CI.
 
Number and percentage of subjects experiencing fatal SAEs, classified by MedDRA Primary System Organ Class and Preferred Term will be tabulated using date of onset of SAE for the time periods—from first vaccination up to 30 days post last vaccination and first vaccination up to 12 months post last vaccination and from study start up to study end will be presented with 95% CI. Fatal SAEs will also be tabulated using the date of death within the same time periods.
 
Number and percentage of fatal SAEs causally related to vaccination for the interval— starting from first vaccination up to 30 days post last vaccination and from first vaccination up to 12 months post last vaccination and from study start up to study end will be presented with 95% CI.
 
Number and percentage of pIMDs from first vaccination up to 12 months post last vaccination will be presented with 95% CI. The same tabulation will also be done for the interval, starting from first vaccination up to 30 days post last vaccination.
 
Number and percentage of pIMDs causally related to vaccination from first vaccination up to 12 months post last vaccination will be presented with 95% CI. The same tabulation will also be done for the interval starting from first vaccination up to 30 days post last vaccination and, for serious pIMDs causally related to vaccination, after 12 months post last vaccination up to study end. (Amended, 23 November 2020)
 
The proportion of subjects with concomitant medication will be tabulated, within 30 days post vaccination and overall, with exact 95% CI.
 
Listing of fatal SAEs, SAEs, pIMDs and withdrawals (from the study or from vaccination) due to AEs, SAEs, solicited and unsolicited AEs will be generated for corresponding follow-up period. Listing of pregnancy during the entire study period will be generated. Listing for all the suspected HZ episodes will be generated.

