3. STUDY DESIGN

Figure 1 Study design overview

CC1 [REDACTED]; N= number of subjects planned to be enrolled; Vacc= Vaccination
RZV= Recombinant Zoster Vaccine

CC1 [REDACTED]
‡ All subjects will be followed-up until last enrolled subject has completed 1 year of follow-up post last vaccination. In case criteria for vaccine efficacy analyses are not met during this period, the follow-up will be extended.

- **Experimental design:** Phase IV, randomized, observer-blind, placebo-controlled, multi-centric, single-country study with 2 parallel groups.
- **Duration of the study:** The duration of the study will vary for each subject. The duration of the study will be up to the study conclusion contact that occurs within 30 days of the projected study conclusion date of the last enrolled subject, that is, 14 months (approximately 430 days) from the enrolment date. Therefore, subjects enrolled early in the trial will be followed for longer duration than the subjects who enrol later in the trial. In case criteria for VE analyses are not met during this period, the follow-up will be extended.

The study conclusion visit/ contact for subjects with an ongoing episode of HZ at the time of last subject last contact will occur at Visit HZ-5 (Day HZ-29).

- **Epoch 001 (Vaccination phase):** Starting at Visit 1 (Day 1) until Visit 3 (Month 3) at one month post last vaccination.
- **Epoch 002 (Follow-up phase):** Starting with the first monthly contact after Visit 3 (Month 3) and ending at the monthly contact that occurs within 30 days of the projected study conclusion date of the last enrolled subject, that is, 14 months (approximately 430 days) from the enrolment date of the last enrolled subject.
- **Primary completion Date (PCD):** The primary completion date will be when the last subject completes his/her study conclusion contact (within 30 days of the projected study conclusion date of the last enrolled subject, that is, 14 months (approximately 430 days) from the enrolment date. In case criteria for VE analyses are not met during this period, the follow-up will be extended.

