The percentage of subjects with at least 1 report of unsolicited AE (including cellulitis) classified by MedDRA primary system organ class (SOC) and preferred terms (PT) will be reported within 30 days (Days 1-30) post each vaccination with exact 95% CI. The same tabulation will be performed for grade 3 unsolicited AEs, for unsolicited AEs with a relationship to vaccination, grade 3 unsolicited AEs with a relationship to vaccination.

Number and percentage of any, grade 3, related, grade 3 related and medically attended unsolicited AEs reported within 30 days (Days 1-30) post *any* vaccination according to MedDRA primary system organ class and preferred terms will be presented.

Number and percentage of SAEs from first vaccination up to 12 months post last vaccination will be presented with 95% CI. The same tabulation will also be done for the interval- starting from first vaccination up to 30 days post last vaccination.

Number and percentage of SAEs causally related to vaccination for the interval- starting from first vaccination up to 30 days post last vaccination and from first vaccination up to 12 months post last vaccination and from study start up to study end will be presented with 95% CI.

Number and percentage of subjects experiencing fatal SAEs, classified by MedDRA Primary System Organ Class and Preferred Term will be tabulated using date of onset of SAE for the time periods –from first vaccination up to 30 days post last vaccination and first vaccination up to 12 months post last will be presented with 95% CI.

Number and percentage of fatal SAEs causally related to vaccination for the interval- starting from first vaccination up to 30 days post last vaccination and from first vaccination up to 12 months post last vaccination and from study start up to study end will be presented with 95% CI.

Number and percentage of pIMDs from first vaccination up to 12 months post last vaccination will be presented with 95% CI. The same tabulation will also be done for the interval – starting from first vaccination up to 30 days post last vaccination.

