5.7.2. Additional considerations

The table on solicited local and general AEs will be presented separately according to GSK grading and grading scale provided by Chinese authorities.

Duration of each solicited local and general AE during the solicited follow-up period will be presented. Total duration of each individual solicited local and general AE will be tabulated.

Duration of each grade 3 solicited local and general AE during the solicited follow-up period will be presented in the table by GSK grading. Duration of each grade 3 and above solicited local and general AE during the solicited follow-up period will be presented in the table by Chinese authority grading.

Listing of complication related to confirmed HZ episode will be presented.

Number and percentage of subjects experiencing fatal SAEs, classified by MedDRA Primary System Organ Class and Preferred Term will be tabulated using date of onset of SAE from study start up to study end will be presented with 95% CI for web disclosure.

The table for web disclosure related to ***solicited adverse events*** endpoint will be based on both GSK and Chinese intensity scale.

Summary of subjects with serious adverse events related to study participation and not by the study vaccines or to GlaxoSmithKline concomitant medication/vaccine during the entire study period based on ES.

Following listings of concomitant medications related to confirmed HZ episode will be presented based on Exposed Set:

- ***Pain rescue medication to control HZ pain***
- ***Antiviral treatment for HZ***
- ***Other therapy for HZ***

Additional analyses/considerations due to COVID-19 pandemic on ES:

- ***Summary of COVID-19 Assessment.***
- ***Incidence of COVID-19 as an AE and SAE. A standardized MedDRA Query (SMQ) will be used to identify all COVID-19 cases reported as AEs.***
- ***A column to identify COVID-19 AEs/SAEs will be added to listing of (S)AEs and solicited adverse events leading to study or treatment discontinuation from first vaccination up to study end.***

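### SAP section 8 drops the protocol's tabulation of fatal SAEs by date of death without a reason, so no planned table gives deaths that occurred within the 30-day or 12-month window

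*SAP*

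**What the plan says.** **Endpoints.** Protocol section 4 (Table 7) lists among the secondary safety endpoints "Occurrence and relationship to vaccination of fatal SAEs from Day 1 up to 30 days post last vaccination" and "Occurrence and relationship to vaccination of fatal SAEs from Day 1 up to 12 months post last vaccination". Neither says whether the onset or the death must fall inside the period.

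**Protocol analysis.** Section 10.3.5 tabulates fatal SAEs by onset date for three periods: to 30 days after the last vaccination, to 12 months after it, and to study end. It then adds: "Fatal SAEs will also be tabulated using the date of death within the same time periods".

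**SAP analysis.** Section 5.7.1 keeps the onset basis, "will be tabulated using date of onset of SAE for the time periods", for the 30-day and 12-month periods; the latter ends with "first vaccination up to 12 months post last will be presented with 95% CI". Section 5.7.2 keeps a study-end table for web disclosure, "will be tabulated using date of onset of SAE from study start up to study end". Section 8 lists the removal of the second tabulation as a change from the protocol: "Fatal SAEs will not be tabulated using the date of death within the same time periods". No reason is given.

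**Follow-up.** SAP section 3 states that "subjects enrolled early in the trial will be followed for longer duration than the subjects who enrol later in the trial". SAP 7.1 continues monthly contacts until 27 confirmed HZ cases have accrued, if that comes after the 12-month safety follow-up. Protocol 12.5.11.1 has unresolved SAEs reviewed until the subject's last visit.

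**Listing.** SAP 5.7.1 keeps an individual listing of fatal SAEs.

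**The concern.** A table of fatal SAEs up to 30 days after the last dose is easily read as a count of deaths in that period. On the onset basis it is a count of SAEs that began in the period and proved fatal at some point while the subject was still being followed. An SAE that starts on Day 20 and is fatal a year later belongs in the 30-day table.

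The 12-month table has a further feature. An SAE that starts in month 11 and is fatal in month 16 is counted if the subject's follow-up reaches month 16. It may be missed if follow-up ended at month 14. The figure therefore has no fixed time horizon.

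The date-of-death table has one, and it needs no observation beyond the window. The protocol planned it for a stated secondary safety endpoint of a post-licensure study. At stake is whether the report contains a fixed-horizon mortality figure by group, with a confidence interval.

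**Working it through.** **1. The plan's own follow-up figure.** Protocol 5.2 gives 14 months, approximately 430 days, for the last enrolled subject. From the optimal intervals in protocol Table 5: 60 + 365 = 425 days. From calendar months: 14 × 30.4375 = 426 days. The stated figure is reproduced to within about 1%.

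**2. How far follow-up runs past each window.** Counting from dose 1, the 30-day window closes at about 60 + 30 = 90 days and the 12-month window at about 60 + 365 = 425 days. The first-subject dates in SAP 9.2.3 run from 14 May 2021 to 15 September 2021, a gap of 124 days. A subject enrolled 124 days before the last one has 430 + 124 = 554 days.

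| Subject | Follow-up | After 30-day window | After 12-month window |
|---|---|---|---|
| Last enrolled | 430 days | 340 days | 5 days |
| Enrolled 124 days earlier | 554 days | 464 days | 129 days |

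A death in these tails, from an SAE with onset inside the window, enters the onset-date table and would not enter a date-of-death table.

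**3. Size.** The documents give no onset-to-death delay. Assume onset uniform over a window of W days, an exponential delay with mean m days, and deaths observed up to day F. Among SAEs with onset in the window that will prove fatal, the fractions counted are:

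- by onset: O = 1 − (m/W)[exp(−(F−W)/m) − exp(−F/m)]
- by date of death: D = 1 − (m/W)[1 − exp(−W/m)]

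Example with W = 90, m = 90, F = 430: O = 1 − (0.0229 − 0.0084) = 0.986; D = 1 − (1 − 0.368) = 0.368; ratio 0.986/0.368 = 2.68.

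Ratio O/D. The 627-day column is an illustrative longer follow-up, from 14 May 2021 to 31 January 2023, the last pandemic-period end in SAP 9.2.3.

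| Window | Mean delay | F = 430 | F = 554 | F = 627 |
|---|---|---|---|---|
| 30-day | 14 days | 1.18 | 1.18 | 1.18 |
| 30-day | 30 days | 1.46 | 1.46 | 1.46 |
| 30-day | 90 days | 2.68 | 2.71 | 2.71 |
| 30-day | 180 days | 4.13 | 4.41 | 4.51 |
| 12-month | 14 days | 1.01 | 1.03 | 1.03 |
| 12-month | 30 days | 1.01 | 1.07 | 1.08 |
| 12-month | 90 days | 1.01 | 1.20 | 1.24 |
| 12-month | 180 days | 1.02 | 1.32 | 1.42 |

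**4. Dependence on follow-up length.** Onset count at F = 554 divided by onset count at F = 430, for mean delays of 14, 30, 90 and 180 days:

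- 12-month table: 1.02, 1.06, 1.19, 1.30
- 30-day table: 1.00, 1.00, 1.01, 1.07

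**5. In events.** The fatal-SAE rate is also an assumption. At 0.5% per year and 3069 subjects per arm, the 30-day window (3 months from dose 1) holds 3069 × 0.005 × 3/12 = 3.84 onsets. With a 90-day mean delay, about 3.84 × 0.986 = 3.8 are counted by onset and 3.84 × 0.368 = 1.4 by death, per arm. At 1% per year both double.

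**6. Other planned tables.** The tables of related fatal SAEs cover related events only, and neither document states their date basis, so they do not supply the missing count.

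**The case against.** The strongest reply is that the SAP changes nothing in the onset-date figure. The protocol already had that table, with the same open end, and the endpoint wording allows the onset reading. The onset count is also the inclusive one: SAEs are collected from the first dose, so a death inside the window from a collected SAE also had its onset inside the window and is counted. All of this stands. A reader might infer that the SAP change causes late deaths to enter the rates; it does not. It removes the companion table that would show how many there are.

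A reader might also suspect a hidden or data-driven deletion. The documents do not support that. The change is declared in the section meant for such changes. It is absent from the list of Amendment 1 changes in SAP section 1, which points to the initial SAP of 8 February 2021, before the earliest centre start shown (14 May 2021).

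Nor do the documents support saying that both windows depend materially on enrolment date. Under the assumed delays the 30-day table moves by 0 to 7%. For a last-enrolled subject the 12-month ratio is only 1.01 to 1.02. Protocol 12.5.11.2 also provides some follow-up of SAEs after discharge, which may capture later deaths. That would weaken the dependence on follow-up length, though it would add post-window deaths to the onset count.

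A biased comparison between arms is not supported either. Allocation is 1:1 and observer-blind, follow-up length should be similar in both arms, and the safety analyses are descriptive.

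Finally, the fatal SAE listing remains and may permit a hand count. Its layout is in a separate document (SAP 10.2), so whether it shows dates of death is unknown. A listing is in any case not a by-group percentage with a confidence interval.

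**Conclusion.** The point holds as an unexplained loss of a protocol-planned safety table. The remaining tables can include deaths after the window, and that they do so cannot be claimed, because the documents contain no data on deaths or delays.

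The ratios rest on uniform onset, an exponential delay and observation ending with the subject's follow-up. The upper end of the 30-day range is driven by the longest assumed delay. The 12-month range of about 1.01 to 1.3 is for follow-up of 430 to 554 days. Follow-up length alone moves the 12-month onset count by 2% to 30% between those two subjects.

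The consequence is for the interpretation of absolute fatal-SAE rates. The primary objective and the between-arm safety comparison are not at risk. It is a cheap improvement that should be made.

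**What to change.** 1. Delete the line on date of death from SAP section 8.
2. In SAP 5.7.1, reinstate the tabulation of fatal SAEs by date of death, by group with 95% CI, from first vaccination to 30 days and to 12 months after the last vaccination, beside the onset-date tables.
3. Label the onset-date tables 'onset in window, fatal at any time up to study end'.

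If the sponsor prefers to keep the change, the least that is needed is a stated reason in section 8 and the label in item 3. That would remove the risk of misreading but would still leave no in-window death count.

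Cost: SAP wording and a few additional safety tables. The protocol already planned this tabulation, so no new data collection and no change to trial conduct should be needed.
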